6.2.3 Renal toxicity

- Grade I: No dose adjustment is required.
- Grade II: Hold therapy until Grade II toxicity resolves. Restart therapy at 50% dose reduction. If well-tolerated, full dose may be administered.

6.2.4 Hepatotoxicity

- Grade I-II: No dose adjustment is required.
- Grade III (AST/ALT >5x ULN): Hold therapy until Grade III toxicity resolves if clearly related to azacitidine administration. Otherwise, consider 50% dose reduction and close monitoring.

6.2.5 For other toxicities, repeat test twice weekly:

- If abnormality resolves within 2 weeks, restart azacitidine at 50% dose reduction ($20\text{mg}/\text{m}^2$) to complete 4 doses. Proceed with DLI after 4th dose.
- If abnormality does not resolve after 2 weeks, hold azacitidine but proceed with DLI if no signs / symptoms of GVHD. Azacitidine 50% dose reduction should be used at start of next cycle even if lab abnormality returns to baseline.

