5.7 Schedule of azacitidine administration

Azacitidine may be held or dose-adjusted based on the parameters below. If azacitidine is held > 6 weeks, the patient will remain on study but will be included in a separate analysis with regard to safety and efficacy.

5.7.1 Cytopenias prior to Cycle 1 require dose reductions as outlined below. Cytopenias following subsequent cycles require dose adjustments based on nadir counts as outlined in appendix 5.

- For platelets $< 30,000/\mu\text{L}$, 50% dose reduction is recommended.
- If platelet transfusion dependent, hold therapy until platelets $> 30,000/\mu\text{L}$.
- For neutrophils < 750 not responsive to GCSF, 50% dose reduction is recommended.
- For neutrophils < 500 not responsive to GCSF, hold therapy until toxicity improves.

5.7.2 Renal insufficiency:

- Creatinine $< 2X$ baseline: No dose adjustment is required.
- Creatinine 2-3X above baseline: Hold therapy until AKI resolves. Restart therapy at 50% dose reduction. If well-tolerated, full dose may be administered.

5.7.3 Hepatotoxicity:

- AST/ALT <5x ULN: No dose adjustment is required.
- AST/ALT 5-20x ULN: Hold therapy until transaminitis resolves. May consider 50% dose reduction and close monitoring.
- AST/ALT >20x ULN: Hold therapy until transaminitis resolves
- Total bilirubin 3-10x ULN: Hold therapy until resolution; may consider 50% dose reduction and close monitoring
- Total bilirubin >10x ULN: Hold therapy until resolution.

5.7.4 For other toxicities, repeat test twice weekly:

- Other laboratory abnormalities to be evaluated on a per-patient basis. Options include holding azacitidine until resolution, versus starting azacitidine at 50% dose reduction at the PI and treating physician's discretion.

5.7.5 Except for ALL patients classified as Low Risk, administration of azacitidine will commence during SWI or FWI if criteria are met (see section 6.2 for dose adjustment guidelines).

- Azacitidine will be given at a dose of 40mg /m² IV or SC daily for 4 days

5.7.6 Administration of azacitidine following SWI or FWI:

- PB and BM chimerism and MRD will be obtained as above and risk will be reassessed.
- No Intervention: For Low Risk ALL patients, azacitidine will be deferred. Patients will receive standard treatment and will be followed by BM every 3 months for 9-12 months.

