- Azacitidine without DLI: Patients meeting Standard Risk criteria will receive azacitidine without DLI at a dose of 40mg/m² IV or SC x 4 days every 6 weeks. DLI should be considered for patients with resolved Grade 2 GHVD if pre- or post-transplant MRD is positive.
- Azacitidine with DLI: Patients meeting High Risk criteria, who also have available cells, will receive DLI in addition to azacitidine. Patients with history of Grade 2 GVHD (which has resolved) may also receive DLI if pre- or post-transplant MRD is positive at the discretion of the treating physician.
 - Administration of azacitidine following withdrawal of immunosuppression will commence (typically on a Monday) 2-8 weeks following *completion* of SWI/FWI (see section 6.2 for dose adjustments).
 - Azacitidine will be given at a dose of 40mg /m² IV or SC daily for 4 days every 6 weeks.
 - Escalating doses of DLI will be administered (typically on a Friday) within 5 days following the last dose of azacitidine every cycle (see section 5.8 for DLI schedule).
 - For patients with negative pre- and post-transplant MRD:
 - Once MDC resolves to FDC in both blood and bone marrow, DLI will be discontinued and patient will continue to receive azacitidine alone for a maximum of 7 cycles as tolerated.
 - If FDC is detected in blood, bone marrow chimerism must be obtained and confirmed to be mixed before proceeding with DLI.
- If DLI is administered without azacitidine during cycles 2 through 7, the subject should continue with all subsequent study assessments, but will be analyzed separately with regard to safety and efficacy.
- Cycles may be delayed for reasons such as toxicity, as per dose adjustment section 6.0.
- For all patients who receive azacitidine, a total of 7 cycles may be administered as tolerated.

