6.2 Azacitidine Toxicity

Guidelines for adjusting azacitidine dose administration are based on the Common Terminology Criteria for Adverse Events (CTCAE version 4.0) applied to patient reports, history and physical, and laboratory evaluations performed each cycle. Laboratory evaluations for toxicity will be performed the week prior to each cycle. Dose adjustments are as follows (28):

- 6.2.1 Development of drug-related grade 4 organ toxicity or severe infection:
 - Discontinuation of azacitidine

- 6.2.2 Hematologic toxicity:
 - Grade I-II toxicity: No dose adjustment is required.

- For platelets <30,000/uL on a stable transfusion regimen, 50% dose reduction is recommended.
- For platelets <15,000/uL, hold therapy until toxicity improves.
- For neutrophils <750 not responsive to GCSF, 50% dose reduction is recommended.
- For neutrophils <500 not responsive to GCSF, hold therapy until toxicity improves.
- See Appendix 5 for guidelines on subsequent dose adjustments based on nadir counts.

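### For AST/ALT 5-20x ULN, 5.7.3 and Appendix 4 hold azacitidine whatever the cause but 6.2.4 does not; separately, the top liver tiers omit the 6.2.1 stop

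*Combined protocol and SAP*

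**What the plan says.** Three places in the protocol tell the investigator what to do about liver toxicity.

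- **Section 5.7** opens with "Azacitidine may be held or dose-adjusted based on the parameters below", so its tiers operate in their own right. Section 5.7.3 then says "AST/ALT 5-20x ULN: Hold therapy until transaminitis resolves. May consider 50% dose reduction and close monitoring". Its top tiers are AST/ALT above 20x ULN, with a hold until resolution, and "Total bilirubin >10x ULN: Hold therapy until resolution".
- **Appendix 4**, the dosing sheet, repeats the liver tiers of 5.7.3. It has a field for the cycle number.
- **Section 6.2** gives dose-adjustment guidelines graded by CTCAE v4.0. For "Development of drug-related grade 4 organ toxicity or severe infection", 6.2.1 prescribes "Discontinuation of azacitidine". For Grade III hepatotoxicity, which it sets at AST/ALT above 5x ULN, 6.2.4 says "Hold therapy until Grade III toxicity resolves if clearly related to azacitidine administration. Otherwise, consider 50% dose reduction and close monitoring".

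Four cross-references lead to Section 6. In 5.7.5, azacitidine is to "commence during SWI or FWI if criteria are met (see section 6.2 for dose adjustment guidelines"). Section 5.7.6 has two more, one on the start of dosing after immunosuppression is withdrawn and one on delayed cycles. The fourth is in the Appendix 4 note on the timing of cycle 2.

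**The concern.** The same laboratory result can lead to different actions depending on which page the site opens. For an AST/ALT of 5-20x ULN that is not clearly due to azacitidine, one site could hold the drug and another could give it, and both could cite the protocol. That matters for the child. It also matters for the data, because holds and dose reductions feed into how patients are counted. More than two dose reductions is a primary safety endpoint (8.3.5), and a hold of more than six weeks moves the patient into a separate analysis of safety and efficacy (5.7).

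The second issue is an omission. The sheet used to give the drug lists what to do at the highest liver values and never mentions that a drug-related grade 4 event ends azacitidine under 6.2.1. Section 11.16.3 lists azacitidine-related grade IV organ toxicity among the events that can trigger the study stopping rules, so this is not a minor event to leave off the sheet.

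**Working it through.** The plan states no figure to reproduce. The check sets the texts side by side.

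| Situation | 5.7.3 and Appendix 4 | Section 6.2 |
|---|---|---|
| AST/ALT 5-20x ULN, not clearly related | Hold; 50% dose may be considered | 6.2.4: no hold required; 50% dose to be considered |
| AST/ALT 5-20x ULN, clearly related | Hold until the transaminitis has resolved; 50% dose may be considered | 6.2.4: hold until the Grade III toxicity has resolved |
| Drug-related grade 4 liver toxicity | Hold until resolution | 6.2.1: discontinue |

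**Row 1.** The actions differ. Attribution decides under 6.2.4 and plays no part in 5.7.3 or Appendix 4. The latter two also leave open whether the 50% dose replaces the hold or follows it. The renal rule in 5.7.2 does settle that order: hold, then restart at 50%.

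**Row 2.** All three texts hold, but to different end points. Take a clearly related rise that falls from 8x to 4x ULN. It is now below the 5x level at which 6.2.4 places Grade III, so the 6.2.4 hold can end. Section 5.7.3 does not define resolution. A reader may take 4x as unresolved, or may point to the 5.7.3 tier that requires no adjustment below 5x.

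**Row 3.** This needs no outside grade 4 cut-off. Section 6.2.4 starts Grade III at AST/ALT above 5x ULN, so any grade 4 AST/ALT value falls in a 5.7.3 tier whose action is to hold. Every bilirubin tier printed in 5.7.3 also says hold. No liver tier in either place says discontinue.

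**Does an order of precedence settle it?** If 6.2 governs, the dosing sheet is wrong in row 1, because it requires a hold that 6.2.4 does not. Section 5.7.3 could not simply be set aside either, since 6.2.4 prints no bilirubin thresholds. If the sheet governs, the 6.2.1 discontinuation is lost. Neither order makes all three texts agree.

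**Do the liver tiers apply only before Cycle 1?** No. That limit is written for cytopenias alone, and Appendix 4 is completed by cycle.

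**Effect on the data, by two hypothetical courses:**

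- Three separate unrelated rises of 5-20x. Under 6.2.4 with the 50% dose taken each time, there are 3 reductions, and 3 > 2 meets 8.3.5. Under 5.7.3 with a hold and full dose on restart, there are 0 reductions. This assumes that a hold is not itself counted as a reduction, which 8.3.5 does not say.
- One unrelated rise that takes more than six weeks to resolve. Under 5.7.3 the patient is held for over six weeks and goes to the separate analysis. Under 6.2.4 dosing can continue and the patient does not.

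**The case against.** The strongest defence concerns the grade 4 issue. The liver tiers act on a laboratory value whatever its cause, while 6.2.1 adds a rule for the drug-related subset. Holding on the value and discontinuing once the event is judged drug-related satisfies both. Section 6 is the titled section for toxicity management, and four pointers lead to it. CTCAE v4.0 is adopted by name, so the absence of a printed grade 4 cut-off is not a gap. Section 11.16 requires such an event to be reported to the Study Chair within 24 hours, and 11.17 gives the judgment on causation to the DSMC.

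Most of that stands. A reader might infer that the protocol contradicts itself on whether to stop the drug, and the documents do not support that. What remains is narrower. None of the four pointers sits in a liver bullet, none states precedence, and the sheet's top tiers end at a hold.

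Two attempts to put a size on the problem also fail. One might count the remaining cycles of seven to cap the further exposure if dosing resumed, but 5.8.4 lets azacitidine continue after cycle 7 in MRD-positive patients. One might also treat a hold as a lost cycle, but the text holds until resolution and 5.7.6 speaks of delayed cycles, so the dose may be given later.

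On the 5-20x band, the defence is that both texts use discretionary language about the 50% dose and that 6.2 calls its rules guidelines. That softens the difference but does not remove it, because the hold in 5.7.3 is not worded as optional.

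**Conclusion.** The 5-20x discrepancy is real: two texts hold for rises not clearly related to azacitidine and the third does not require it. For clearly related rises all three hold, but to different end points. In this band the dosing sheet is the more cautious text. The grade 4 issue is an omission from 5.7.3 and Appendix 4 that can be reconciled with 6.2.1. A site relying on the liver bullets alone could still resume dosing.

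The size cannot be put in numbers, because the documents do not say how often either event is expected. The sample size calculation does not depend on these rules. It would be too strong to conclude that the efficacy analysis is untouched, since the six-week provision in 5.7 covers efficacy as well as safety. How many patients would move, and in which direction the results would shift, is unknown.

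Resumption after a grade 4 event is not in itself proof of an error, because 11.11 allows re-challenge after stopping for selected events. The protocol does not say whether a drug-related grade 4 liver event is one of them.

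This should be corrected. It does not undermine the design.

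**What to change.** - **One AST/ALT 5-20x rule in 5.7.3, 6.2.4 and Appendix 4.** Align 6.2.4 to the hold already in the other two. Give the hold a single defined end point, and state that the 50% dose applies on restart.
- **A line in the liver tiers of 5.7.3 and Appendix 4:** *if drug-related CTCAE v4.0 grade 4, discontinue azacitidine per 6.2.1.* State there whether re-challenge under 11.11 can apply.

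The cost is amended wording in three places and a reissued dosing sheet. The clinical price of the cautious rule is that some doses will be delayed for rises that azacitidine did not cause. If the sponsor prefers attribution to decide, it should say so in all three places.

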7.0 Criteria for Termination

7.1 Conditions for terminating the study:

The PI may terminate the study for any of the following reasons:

- 7.1.1 Significant toxicities are observed.
- 7.1.2 Stopping rules for interim toxicity and relapse futility are triggered as per Section 8.7.3.
- 7.1.3 It becomes clear that the study treatment is less effective than standard treatment.
- 7.1.4 All data have been collected.

7.2 Conditions for terminating individual patient participation in the study:

The PI may terminate the participation of an individual patient for any of the following reasons:

- 7.2.1 Withdrawal from the study by patient / parents or physician
- 7.2.2 Death
- 7.2.3 Leukemia relapse, defined as >5% leukemic blasts on bone marrow examination or more than 1% leukemic cells by immunoflow or FISH.
- 7.2.4 Loss to follow-up or non-compliance with study procedures.

8.0 Statistical Considerations

8.1 Primary Efficacy endpoint definitions

- 8.1.1 Relapse rate

8.2 Secondary / Exploratory endpoints

- 8.2.1 Relapse-free survival
- 8.2.2 Median time to relapse

8.3 Primary Safety Endpoint Definitions

- 8.3.1 National Cancer Institute CTCAE version 4.0 grade 3 or higher renal, hepatic, cardiac, pulmonary, or neurologic toxicity;
- 8.3.2 Grade III/IV acute GVHD or Severe/Extensive chronic GVHD
- 8.3.3 Serious infection
- 8.3.4 Severe hematologic toxicity/ graft failure
- 8.3.5 >2 dose reductions for any reason.

8.4 Sample size

- 8.4.1 The sample size is estimated using Bayesian sequential monitoring design with toxicity and response outcomes as multiple endpoints(45). It is assumed that the rate of relapse in pediatric acute leukemia post-transplant would be 40% (as shown in our pilot study), azacitidine +/- DLI would reduce the 2-year relapse rate by approximately 40% to a rate of 25%. A sample size of 67 evaluable patients is required to provide 80% power at a one-sided significance level of 0.05 to test the hypothesis based on the relapse rate of H0: relapse rate > 40% (historically-controlled) versus Ha: relapse rate < 25% (treatment-targeted). The study will enroll patients until accrual of 67 patients is achieved.
- 8.4.2 Enrollment of 67 patients will be attainable with enrollment at multiple centers. Investigators from All Children's Hospital, Lucille Packard Children's Hospital have written letters of support expecting to enroll 30-40 patients over 2 years.

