1.11 Preliminary data

Our group has been studying the use of subset chimerism testing and pre-emptive immunotherapy with fast withdrawal of immunosuppression (FWI) and donor lymphocyte infusion (DLI) since 2005. Our prospective multi-institutional study evaluated the feasibility of longitudinal chimerism testing in a central laboratory (including WB, CD3+, and leukemia-specific lineage chimerism) in patients with a variety of hematologic malignancies, and evaluated the feasibility of fast withdrawal of immunosuppression based on WB chimerism results. Centralized chimerism testing was feasible and showed low inter-assay variability. Increasing mixed chimerism (MC) in WB was not useful as a predictor of relapse in our study. The presence of full donor chimerism in WB, CD3+ and leukemia-specific lineages on all measurements was related to a significantly lower risk of relapse than the presence of MC in either subset (11% vs 71%, respectively; P=0.03). Increasing host chimerism in leukemia-specific lineage heralds relapse, but it was not detected early enough to allow immunotherapy. The conclusion of the study was that the goal of preemptive immunotherapy should be to achieve full donor chimerism in WB in CD3+ and leukemia-specific lineages, in an effort to prevent relapse before donor chimerism declines (40).

In a recent prospective UCSF analysis, 43 children (25 AML, 18 ALL,) underwent myeloablative BMT or PBSCT followed by immunomodulatory therapy (IT) between 2009 and 2012 (44). Patients with FDC in BM and PB at day 30 or evidence of GVHD were assigned to observation only (N=12). Patients with mixed chimerism (regardless of MRD) were assigned to intervention. Intervention consisted of fast withdrawal of immunosuppression (FWI) in 26 patients; 14 of these also received DLI. Five patients could not be assigned due to early death or relapse. Overall survival at a median of 30 months was 54%. Toxicity was acceptable, with an acute GVHD rate of 19% in the intervention arm, and a toxic death rate of 4%. Relapse was observed in 10/38 patients; 8 of the 10 relapses occurred in the intervention arm (associated with mixed chimerism). Four of these occurred late at >24 months post-transplant.

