8.7.3 Stopping rules for interim toxicity and relapse futility

- Study data will be analyzed for relapse rates within 3 months for efficacy assessment. Such early futility assessment will be done when the first 14 patients have completed the 3-month follow-up in the study. If there are 9 or more relapses out of 14 patients during the futility assessment, enrollment will be stopped due to futility. Otherwise an additional 54 patients will be accrued for a total of 67 patients in the study. By the end of the study, if there are 32 or more relapses observed, further investigation will not proceed. In this study the rate of relapse in pediatric acute leukemia post-transplant is assumed to be 40% (as shown in our pilot study), azacitidine +/- DLI would reduce the 2-year relapse rate by approximately 40% to a rate of 25% and that the toxicity rate in pediatric acute leukemia post-transplant under azacitidine +/- DLI would be 20%. The stopping rules for toxicity and relapse rate under sequential design of multiple endpoints are shown below:
- For patients receiving DLI, a subset analysis of incidence of Grade III-IV aGVHD and mortality secondary to GVHD will be performed when a new patient is diagnosed with Grade III-IV GVHD or chronic GVHD.
 - Reported rates of grade III-IV acute GVHD following DLI range from 20-35%; GVHD-related mortality ranges from 5-15%.
 - If rates of Grade III-IV aGVHD or GVHD-related mortality in this study exceed published rates, enrollment and further DLI administration will be suspended while further safety analysis is performed.

Patients on Study	<14	15-21	22-28	29-35	36-42	43-49	50-56	57-63
Number of patients with SAE (Toxicity)	>8	≥10	≥13	≥16	≥18	≥21	≥23	≥26
Number of patients with relapse in 3 months	>9	≥13	≥16	≥19	≥23	≥26	≥29	≥32

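### The 40% null relapse rate is credited to a pilot whose reported results do not show it, and the end-of-study criteria do not match the stated test of 40% against 25%

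*Combined protocol and SAP*

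**What the plan says.** - **The null.** Section 8.4.1: "It is assumed that the rate of relapse in pediatric acute leukemia post-transplant would be 40% (as shown in our pilot study"). Section 8.7.3 says the same: "In this study the rate of relapse in pediatric acute leukemia post-transplant is assumed to be 40% (as shown in our pilot study"). Neither names the pilot.
- **The test.** Section 8.4.1 asks for 67 evaluable patients, 80% power and one-sided 0.05 for "H0: relapse rate > 40% (historically-controlled) versus Ha: relapse rate < 25% (treatment-targeted"). The 25% target is a 2-year rate. No critical number of relapses is given.
- **End-of-study criteria.** The protocol summary calls the study successful if 2-year relapse is below 25% (with limits on GVHD and toxicity). Section 8.7.3 adds: "By the end of the study, if there are 32 or more relapses observed, further investigation will not proceed". Section 8.6.2 plans a proportion with a 95% CI and no test.
- **The group's own data, section 1.11.** For the 2009-2012 cohort of 43 children: "Relapse was observed in 10/38 patients; 8 of the 10 relapses occurred in the intervention arm (associated with mixed chimerism"). On timing: "Four of these occurred late at >24 months post-transplant". On the other five patients: "Five patients could not be assigned due to early death or relapse". On treatment: "Intervention consisted of fast withdrawal of immunosuppression (FWI) in 26 patients; 14 of these also received DLI".

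**The concern.** In a single-arm trial the null rate takes the place of the control arm. Hypothesis 2.3.1 claims a lower 2-year relapse rate than historical controls, and 40% is the only historical value the plan tests against. A reader who follows the reference back to section 1.11 does not find 40% for a whole cohort.

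The second difficulty is the decision. Section 8.4.1 specifies a test by its error rates, while the summary and 8.7.3 state end-of-study thresholds that are not tied to it. Without a stated cut-off, a result of 17, 18 or 19 relapses could be reported either as rejecting 40% or as missing the success criterion, and the choice could be made after the data are seen.

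**Working it through.** **1. Does any reported result of the group show 40%?**

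| Source | Rate | Population |
|---|---|---|
| 1.11, 2009-2012 cohort | 10/38 = 26.3% (exact 95% CI 13.4% to 43.1%) | assigned patients, all follow-up |
| same, none of the five unassigned relapsed | 10/43 = 23.3% | all 43 |
| same, all five relapsed | 15/43 = 34.9% | all 43 |
| 1.11, feasibility study | 11% and 71% | by chimerism; no overall rate |
| 1.11, 2009-2012 cohort | 41%, 38%, 37% | mixed-chimerism subgroups |
| 9.5 | about 70%; 5 of 7 | mixed-chimerism subgroups |

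Outside the group's work, section 1.1 gives 30-40%, at 5 years. Section 1.3 gives 41% in the high-dose arm of a cited cyclosporine comparison. This trial also enrols patients with full donor chimerism and Low-Risk ALL patients (5.3.4), so a mixed-chimerism rate does not describe its population.

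**2. Reproduce N = 67.** With p0 = 0.40 and p1 = 0.25:

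n0 = [(1.645·√(0.40·0.60) + 0.842·√(0.25·0.75)) / 0.15]² = 60.9

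With continuity correction, (n0/4)·[1 + √(1 + 2/(n0·0.15))]² = 67.4. Exact binomial reaches 80.5% power at n = 66. So 67 is consistent with the stated inputs, and the sample-size arithmetic is not in question.

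**3. The cut-off and the stated criteria.** Let X be the number of relapses, binomial with n = 67, with 2-year status known for every patient.

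| Criterion | Count of 67 | Probability at true 40% | Probability at true 25% |
|---|---|---|---|
| Exact one-sided 0.05 test | ≤19 (28.4%) | 0.032 | 0.784 |
| One relapse more | ≤20 (29.9%) | 0.056 | 0.855 |
| Summary: below 25% | ≤16 (23.9%) | 0.004 | 0.481 |
| 8.7.3: no further investigation | ≥32 (47.8%) | 0.121 | <0.001 |

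The count for the summary criterion follows from 16/67 = 23.9% and 17/67 = 25.4%. Its probabilities are before its GVHD and toxicity conditions. A true rate of 40% escapes the rule of 32 or more with probability 1 − 0.121 = 0.88.

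**4. The planned interval.** At 19/67 the exact two-sided 95% upper limit is 40.7%, so the interval includes 40% although the one-sided test rejects it. Section 8.6.2 does not name the interval method. A simple normal interval gives 0.284 + 1.96·√(0.284·0.716/67) = 0.392, which excludes 40%. The reading at the boundary therefore depends on an unstated choice.

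**5. Hypothetical 2-year rates.** These borrow the cohort's all-follow-up figures for illustration only.

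| Assumed true 2-year rate | P(X ≤ 19) | P(X ≤ 16) |
|---|---|---|
| 26.3% (10/38) | 70% | 38% |
| 30.8% (8/26, intervention arm) | 39% | 14% |
| 34.9% (15/43) | 16% | 4% |

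**6. If a sourced null were lower, with n = 67 kept.** Null 35%: reject at 16 or fewer, alpha 0.035, power 48% at 25%. Null 30%: reject at 13 or fewer, alpha 0.035, power 18% at 25%.

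**The case against.** The best defence is that 40% is a reasonable historical figure whatever its label. It is the top of the range in section 1.1, and the cohort's interval reaches 43%. The cohort was AML and ALL only, whereas this trial also takes JMML and MDS. In addition, 26 of the 38 had fast withdrawal of immunosuppression, 14 of them with DLI, so their relapse rate may understate that of untreated controls. The unnamed pilot could also be the feasibility study. Its overall rate would be 40% if (0.40 − 0.11)/(0.71 − 0.11) = 48% of patients had mixed chimerism, and the split is not given. All of this stands. It shows that 40% may be right. It does not show that the protocol supports it, and the range in 1.1 is a 5-year rate from other sources.

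On the cut-off, one can say that 19 or fewer follows from the stated alpha, N and null, and that the summary and 8.7.3 do give end-of-study criteria. The first is true only once an exact binomial test is assumed. Section 8.4.1 names a Bayesian sequential design and does not say how the final test is done. The second is also true, but those criteria have error rates far from the ones stated.

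**Conclusion.** Two limited conclusions hold.

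1. The attribution in 8.4.1 and 8.7.3 is not supported, as reported, for a 2-year null in this population.
2. The stated criteria do not implement the stated test. The summary threshold is much stricter (alpha 0.004, power 48%), and the rule of 32 or more seldom stops a treatment whose true rate equals the null (12%). Nothing is said about 17-19 or 20-31 relapses.

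Three stronger readings are tempting and should not be drawn.

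- **That 40% is disproved.** It is not, for the reasons conceded above.
- **That the cohort's rates fall between the two hypotheses.** The range over all 43 starts at 23.3%, below 25%, and these rates cover all follow-up. Because four of ten relapses came after 24 months, the crude 2-year figure is lower. Its value cannot be given, since censoring, competing deaths and the outcomes of the five unassigned patients are not described. The 70%, 39% and 16% above are therefore conditional illustrations.
- **That rejecting 40% would be a false claim for azacitidine over fast withdrawal with or without DLI.** Objective 2.1.1 and hypothesis 2.3.1 make no such comparison.

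The figures assume an exact binomial test and complete 2-year relapse status in all 67. Severity is minor to moderate: N = 67 stands, but the benchmark and the decision rule need restating.

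**What to change.** 1. **Sections 8.4.1 and 8.7.3.** Replace the pilot attribution with the actual source, its count, population, time point and CI, or remove it. Give the basis for a 2-year null. If that null is below 40%, restate the power that n = 67 provides (step 6 of the working).
2. **Section 8.4.1.** State the cut-off, for example: 40% is rejected if 19 or fewer of 67 patients have relapsed by 2 years (exact one-sided alpha 0.032, power 78% at a true 25%). Reconcile this with the under-25% and 32-or-more criteria, and state the conclusion for 17-19 and for 20-31 relapses. Say whether 32 or more counts 2-year or 3-month relapses, because 32 also appears in the 8.7.3 table row for relapse in 3 months (57-63 patients). If rejection probabilities at 26%, 31% and 35% are shown, label them as hypothetical 2-year rates.
3. **Section 8.6.2.** Name the interval method. Report the 2-year rate and CI beside the 2009-2012 cohort's 24-month rate and CI as context, noting that the cohort was AML and ALL only and mostly had fast withdrawal with or without DLI.

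The cost is rewording in three sections, a short statement of operating characteristics, and one 24-month rate from the group's own data. Enrolment does not change.
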